13.1.1.5 Adverse Event Causality

Every effort will be made by the investigator to assess the relationship of the AE, if any, to the study drug(s). Causality will be classified using the categories presented in Table 13-2.

Table 13-2 Classifications for AE Causality

Classification	Definition
Related	There is an association between the event and the administration of investigational study drug, a plausible mechanism for the event to be related to the investigational study drug and causes other than the investigational study drug have been ruled out, and/or the event re-appeared on re-exposure to the investigational study drug.
Possibly related	There is an association between the event and the administration of the investigational study drug and there is a plausible mechanism for the event to be related to investigational study drug, but there may also be alternative etiology, such as characteristics of the subject's clinical status or underlying disease.
Unlikely related	The event is unlikely to be related to the investigational study drug and likely to be related to factors other than investigational study drug.
Not related	The event is related to an etiology other than the investigational study drug (the alternative etiology will be documented in the study subject's medical record).

13.1.1.6 Study Drug Action Taken

The investigator will classify the study drug action taken with regard to the AE. The action taken will be classified according to the categories shown in Table 13-3.

Table 13-3 Classifications for Study Drug Action Taken With Regard to an AE

Classification	Definition
Dose not changed	Study drug dose not changed in response to an AE
Dose reduced	Study drug dose reduced in response to an AE
Drug interrupted	Study drug administration interrupted in response to an AE
Drug withdrawn	Study drug administration permanently discontinued in response to an AE
Not applicable	Action taken regarding study drug administration does not apply. "Not applicable" will be used in circumstances such as when the investigational treatment had been completed before the AE began and no opportunity to decide whether to continue, interrupt, or withdraw treatment is possible.

13.1.1.7 Adverse Event Outcome

An AE will be followed until the investigator has determined and provided the final outcome. The outcome will be classified according to the categories shown in Table 13-4.

Table 13-4 Classifications for Outcome of an AE

Classification	Definition
Recovered/Resolved	Resolution of an AE with no residual signs or symptoms
Recovered/ Resolved With Sequelae	Resolution of an AE with residual signs or symptoms
Not Recovered/Not Resolved (Continuing)	Either incomplete improvement or no improvement of an AE, such that it remains ongoing
Fatal	Outcome of an AE is death. "Fatal" will be used when death is at least possibly related to the AE.
Unknown	Outcome of an AE is not known (e.g., a subject lost to follow-up)

13.1.1.8 Treatment Given

The investigator ensures adequate medical care is provided to subjects for any AEs, including clinically significant laboratory values related to study drug. In addition, the investigator will describe whether any treatment was given for the AE. "Yes" is used if any treatment was given in response to an AE, and may include treatments such as other medications, hospitalization, surgery, or physical therapy. "No" indicates the absence of any kind of treatment for an AE.

13.1.2 Serious Adverse Events

13.1.2.1 Definition of a Serious Adverse Event

An SAE is any AE that meets any of the following outcomes:

- Fatal (death, regardless of cause, that occurs during participation in the study or occurs after participation in the study and is suspected of being a delayed toxicity due to administration of the study drug)
- Life-threatening, such that the subject was at immediate risk of death from the reaction as it occurred
- Inpatient hospitalization or prolongation of hospitalization
- Persistent or significant disability/incapacity (disability is defined as a substantial disruption of a person's ability to conduct normal life functions)
- Congenital anomaly or birth defect
- Important medical event that, based upon appropriate medical judgment, may jeopardize the subject or may require medical or surgical intervention to prevent 1 of the outcomes listed above (e.g., an allergic bronchospasm requiring intensive treatment in an emergency room or at home)

If a subject has a hospitalization or procedure (e.g., surgery) for an event or condition that occurred before the subject signed the ICF, and the hospitalization or procedure was planned before the subject signed the ICF, the hospitalization or procedure should not be considered to indicate an SAE, unless an AE caused the hospitalization or procedure to be rescheduled sooner or to be prolonged relative to what was planned. In addition, hospitalizations clearly not associated with an AE (e.g., social hospitalization for purposes of respite care) should not be considered to indicate an SAE.

Clarification will be made between the terms “serious” and “severe,” because they are not synonymous. The term “severe” is often used to describe the intensity (severity) of a specific event, as in mild, moderate, or severe myocardial infarction. The event itself, however, may be of relatively minor medical significance, such as a severe headache. This is not the same as “serious,” which is based on subject/event outcome or action described above, and is usually associated with events that pose a threat to a subject's life or functioning. Seriousness, not severity, serves as a guide for defining expedited regulatory reporting obligations.

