- Subjects who completed 24 weeks of study drug treatment (i.e., lumacaftor in combination with ivacaftor or placebo) in Study 109 or completed 24 weeks of study drug treatment and the Week 26 Safety Follow-up in Study 011B (NOTE: the last dose of study drug is the evening dose administered the day before the Week 24 Visit or the dose at the Week 24 Visit [based on the applicable protocol version for which a subject screens (provides consent/assent) under] in Study 109 or the evening dose administered the day before the Week 24 Visit in Study 011B)
- Subjects who are not receiving study drug treatment at the end of the Treatment Period in Study 109 or Study 011B (NOTE: subjects from Study 011B have a planned Washout Period from Week 24 to Week 26 and must still complete the Week 26 Safety Follow-up), including subjects who require study drug interruption to be either continued or initiated at Day 1 in Study 110, AND who have received Vertex approval for entry

Subjects who prematurely discontinued study drug treatment are not eligible for enrollment in the Treatment Cohort.

The Treatment Cohort will be open-label and will consist of the following dose regimens:

- LUM 200 mg q12h/IVA 250 mg q12h (subjects aged 6 through 11 years)
- LUM 400 mg q12h/IVA 250 mg q12h (subjects aged 12 years and older)

Subjects who turn 12 years of age in the previous study or Day 1 of this rollover study will begin receiving LUM 400 mg q12h/IVA 250 mg q12h on Day 1. Subjects who turn 12 years of age after the Day 1 Visit of this rollover study will begin receiving LUM 400 mg q12h/IVA 250 mg q12h at their next scheduled visit.

Observational Cohort

The following subjects from Study 109 or Study 011B who meet the study criteria and elect to enroll in Study 110 are eligible for enrollment in the Observational Cohort:

- Subjects who received at least 4 weeks of study drug in Study 109 or Study 011B and completed visits up to Week 24 of Study 109 or Week 26 of Study 011B but who are not eligible for the Treatment Cohort with lumacaftor in combination with ivacaftor
- Subjects who received at least 4 weeks of study drug in Study 109 or Study 011B (and did not prematurely discontinue study drug treatment) and completed visits up to Week 24 of Study 109 or Week 26 of Study 011B but who elect not to continue treatment with lumacaftor in combination with ivacaftor

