8.1.1 Treatment Cohort

8.1.1.1 Treatment Period

To participate in the study, the subject's parent or legal guardian must sign and date a study-specific informed consent form (ICF) and the subject must sign an assent form (if applicable) before any study-specific procedures can be performed. The ICF (and assent form, if applicable) will comply with all applicable regulations governing the protection of

human subjects and will be approved by Vertex and the site's institutional review board (IRB)/independent ethics committees (IEC).

After obtaining informed consent and assent (where applicable), subjects will receive the following treatment:

- LUM 200 mg q12h/IVA 250 mg q12h (subjects aged 6 through 11 years)
- LUM 400 mg q12h/IVA 250 mg q12h (subjects aged 12 years and older)

Subjects who turn 12 years of age in the previous study or Day 1 of this rollover study will begin receiving LUM 400 mg q12h/IVA 250 mg q12h on Day 1. Subjects who turn 12 years of age after the Day 1 Visit of this rollover study will begin receiving LUM 400 mg q12h/IVA 250 mg q12h at their next scheduled visit.

Dosing details are given in Section 10.

Timing of Day 1 Visit in Study 110 Active Sites

The Day 1 Visit of Study 110 will be on the **same day** as the Week 24 Visit (last Treatment Period visit) of Study 109 or the Week 26 Visit (Safety Follow-up Visit) of Study 011B for subjects at Study 110 sites that have been activated by the time the Week 24 Visit (Study 109) or the Week 26 Visit (Study 011B) has been completed. Subjects at these active sites will NOT have to repeat any Study 110 Day 1 assessments that were specified to be performed at the Week 24 Visit (Study 109) or the Week 26 Visit (Study 011B). Assessments for the Treatment Cohort are listed in Table 3-1. Subjects will be outpatients during the Treatment Period. All visits should occur within the windows specified.

Subjects at these active sites may return within 1 calendar day to complete the remaining Day 1 assessments (including administration of the Day 1 dose for subjects who receive the last Study 109 dose at the Week 24 Visit [see Section 10.2]) specific to Study 110. If study drug administration occurs when a subject returns the following calendar day, predose vital sign and spirometry assessments must be repeated before dosing.

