11.6.7.2 Hospitalization for CF

At visits indicated in [Table 3-1](#), subjects will be queried about planned and unplanned hospitalizations lasting ≥ 24 hours. The dates for hospitalizations and the reasons for hospitalizations will be documented.

If the hospitalization is unplanned, the procedures for safety reporting should also be followed ([Section 13.1.2.3](#)).

The following information will be determined:

- Number of planned hospitalizations for CF (i.e., prophylactic antibiotic therapy)
- Number of all unplanned hospitalizations
- Number of days of all unplanned hospitalizations
- Time-to-first unplanned hospitalization

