13.1.1.3 Documentation of Adverse Events

All ongoing or newly developed AEs at, or after, completion of treatment in Study 109 or Study 011B will be collected until the following time points:

- Withdrawal of consent or through the Safety Follow-up Visit (NOTE: only SAEs will be collected for the Observational Cohort)
- For enrolled subjects who do not have a Safety Follow-up Visit: 28 days after the last dose of study drug

All subjects will be queried, using non-leading questions, about the occurrence of AEs at each study visit. When possible, a constellation of signs and/or symptoms will be identified as 1 overall event or diagnosis. All AEs for enrolled subjects will be recorded in the eCRF and source document. The following data will be documented for each AE:

- Description of the event
- Classification of “serious” or “nonserious”
- Date of first occurrence and date of resolution (if applicable)
- Severity
- Causal relationship to study drug(s)
- Action taken
- Outcome
- Concomitant medication or other treatment given

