9.1.1 Previous Study Period

Previous Study Period starts from the first dose date of study drug in the parent studies (109 and 011B) to up to the first dose date of study drug in Study 110, including 1) the planned 2-week washout period per Study 011B design; or 2) the Roll-Over Gap between the previous studies (Study 109 and Study 011B) and Study 110.

For the majority of the subjects, the first dose of study drug and assessments in Study 110 will happen on the same day as the Week 24 Visit in Study 109 or the Week 26 Visit in Study 011B.

For assessment performed on the first dose day in Study 110:

- If information regarding the assessment timing is available, then the assessment time will be compared to the first dose time in Study 110 to decide whether the assessment is before the first dose, concurrent with the first dose, or after the first dose.
- If information regarding assessment timing is not available, then the record will be included in the Previous Study Period if it comes from the Previous Study database, and the record will be included in the Current Study Period if it comes from the Current Study database.

Treatment-Emergent Period for the Previous Study Period

The treatment-emergent period for the Previous Study Period is the period on or after the first dose of study drug in the previous studies to 28 days after the last dose of the previous studies, or the last day of the Previous Study Period, or up to the first dose date in Study 110 (not including the first dose date in Study 110), whichever occurs first, for subjects dosed in Study 110.

For subjects not dosed in Study 110, the treatment-emergent period will be the period on or after the first dose of study drug in the previous studies to 28 days (inclusive) after the last dose of study drug in the previous studies or to the last day in the previous studies (inclusive), whichever occurs first.

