9.1.3 Cumulative Study Period

Cumulative Study Period starts from the first dose of study drug in the parent studies (109 and 011B) to the last day in Study 110, regardless of whether there is 1) the planned 2-week washout period per Study 011B design; or 2) a Roll-Over Gap between the previous studies (Study 109 and Study 011B) and Study 110. For subjects not enrolled in Study 110, the Cumulative Study Period will be the same as the Previous Study Period.

Treatment-Emergent Period for the Cumulative Study Period

The treatment-emergent period for the Cumulative Study Period is the period on or after the first dose of study drug in the previous studies to 28 days (inclusive) after the last dose of study drug in Study 110, or up to the last day in Study 110, whichever occurs first. For subjects not enrolled in Study 110, the treatment-emergent period for the Cumulative Study Period will be the same as that of the Previous Study Period.

Handling of the data during the gap between previous studies (Study 109 and Study 011B) and the rollover study (Study 110)

There may be a Roll-Over Gap between the previous studies and the rollover study, defined as the time period between the Week 24 Visit of Study 109 or the Week 26 Visit of Study 011B and the date prior to the Day 1 Visit of Study 110. All analyses will be performed regardless of whether there is a Roll-Over Gap between the previous studies (Study 109 and Study 011B) and Study 110.

- This affects summary of the following possibly continuing events: 1) AEs; 2) CMs; and 3) Pulmonary Exacerbation related endpoints: Pulmonary Exacerbations, Pulmonary Exacerbations requiring hospitalizations (planned and unplanned), and Pulmonary Exacerbations requiring IV antibiotics.

Events that happen during the Roll-Over Gap will be included in the Cumulative Study Period related analysis, but not necessarily in the analysis of the previous studies or the Current Study Period for Study 110. There are possible differences between results from Cumulative Study Period and combining results from previous studies and the Study 110.

- The Roll-Over Gap will not be considered in the derivation of the analysis window. The assessments will be selected per windowing rules specified for visits in Study 110 as described in Appendix D. The same set of selected records will be associated with different visit labels for different dosing periods.

9.2 Treatment Cohort Period 2

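### The SAE exemption for pre-planned hospitalizations runs from the Study 110 consent, so an already planned admission for an event that arose on parent-study LUM/IVA can escape serious status

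*Protocol*

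**What the plan says.** Protocol 13.1.2.1 lists inpatient hospitalization as a seriousness criterion and then sets aside admissions and procedures that satisfy both parts of this condition: "event or condition that occurred before the subject signed the ICF, and the hospitalization or procedure was planned before the subject signed the ICF". It restores SAE status in one situation: "unless an AE caused the hospitalization or procedure to be rescheduled sooner or to be prolonged relative to what was planned".

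Protocol 8.1.1.1 and 8.1.2.1 define the ICF as the form specific to this study. The schedules (Tables 3-1 and 3-2) place it at Study 110 Day 1. The exemption does not mention the parent-study consent or the first parent-study dose.

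By then the child has been treated. The Synopsis admits to the Treatment Cohort "Subjects who completed 24 weeks of study drug treatment (i.e., lumacaftor in combination with ivacaftor or placebo) in Study 109", with a matching rule for Study 011B. For most subjects, according to SAP 9.1.1, "the first dose of study drug and assessments in Study 110 will happen on the same day as the Week 24 Visit in Study 109"; for Study 011B the corresponding visit is at Week 26. At sites not yet activated, Day 1 comes later.

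Two other provisions treat parent study and rollover as one safety record. Protocol 13.1.1.3 states: "All ongoing or newly developed AEs at, or after, completion of treatment in Study 109 or Study 011B will be collected". SAP 9.1.3 states: "Cumulative Study Period starts from the first dose of study drug in the parent studies (109 and 011B) to the last day in Study 110".

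**The concern.** An exemption for planned admissions normally keeps conditions that pre-date any study drug out of the SAE count. Here the reference date falls after the parent treatment period, so the exemption also reaches conditions that began on LUM/IVA. The rest of the plan goes the other way: it collects AEs that are ongoing at rollover and counts treatment-emergent events for the L200/I-L/I group from the first parent dose.

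Long-term safety is the primary objective, and serious TEAEs are one of its main summaries. The 24-hour report to the sponsor (Protocol 13.1.2.3) and SAE narratives (SAP 10.5) also depend on SAE status. For the Observational Cohort, SAEs are the only endpoint.

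**Working it through.** The plan gives no figure on this point. Its one precision table (Protocol 12.1) concerns the incidence of CF lung. The check is therefore mainly a reading of the rules together, followed by a scale calculation.

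**1. The case.** A child has an event on LUM/IVA in the parent study. An elective admission or procedure for it is arranged at or before the rollover visit and takes place after Study 110 consent, on the planned date and for the planned length.

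**2. Applying 13.1.2.1.** The condition precedes the Study 110 ICF, and so does the planning. No AE hastened or prolonged the stay. The admission therefore does not indicate an SAE. At a site with a rollover gap the ICF is signed later, so planning done during the gap also qualifies.

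**3. Following the case into the counts.**

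| Output | Effect of the exemption |
|---|---|
| Current Study Period, 110 Safety Set | Little. An event that began before the first Study 110 dose is a TEAE here only if it worsened (SAP 9.1.2, 10.4.1). |
| Cumulative period, L200/I-L/I, feeding L/I Overall | The event stays a TEAE (SAP 9.1.3, 10.1.2.1). Its serious flag is lost unless the parent study set it or another seriousness criterion applies. |
| P-L/I part of L/I Overall | None for on-LUM/IVA events. These children had placebo before the ICF, and only their Study 110 period is pooled. |
| Observational Cohort | Only SAEs are collected (Protocol 13.1.1.3), so there may be no Study 110 event record. |

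Protocol 12.4.4.1 leaves the handling of AEs ongoing at rollover to the SAP. SAP 9.1.3 says that events in the gap enter the cumulative analysis, but not how seriousness is settled when the admission comes after rollover.

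**4. Scale per lost event.** Inputs: 256 potentially eligible children, 200 from Study 109 and 56 from Study 011B (Protocol 12.1); 24 parent weeks and 96 Study 110 weeks; 48 weeks counted as one patient-year (SAP 10.1.2.1). Assumptions: all enrol and complete, and 67 to 100 of the 200 Study 109 children had placebo, because the documents do not give the allocation ratio.

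Patient-years in L/I Overall = (prior-active children × 120 + prior-placebo children × 96) / 48.

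- 67 placebo, 189 active: (189 × 120 + 67 × 96) / 48 = 29,112 / 48 = 606.5.
- 100 placebo, 156 active: (156 × 120 + 100 × 96) / 48 = 28,320 / 48 = 590.0.

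One lost serious TEAE is 100 / 606.5 = 0.16 to 100 / 590.0 = 0.17 per 100 patient-years. Five would be 0.82 to 0.85. One child is 1 / 256 = 0.39% of the eligible total. SAP 10.2.4 counts the 2-week Study 011B washout as exposure; this adds 56 × 2 / 48 = 2.3 patient-years and leaves the per-event figures unchanged to two decimals. Lower enrolment or shorter exposure would raise the effect per event.

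**The case against.** The strongest reply is that the exemption is narrow and its consequences mostly cannot be shown from these documents. Much of this stands.

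- **Both conditions must hold.** A reader might infer that any admission for an event that began on LUM/IVA is exempt. It is not. Unplanned admissions, admissions planned after consent, and stays hastened or prolonged by an AE all remain SAEs. Since most children roll over on the Week 24 or Week 26 visit day, only elective admissions still pending at that point qualify.
- **Only one criterion is removed.** The event can still be serious on another ground, including as an important medical event that may need intervention.
- **The event is not lost in the Treatment Cohort.** A reader might infer that such events drop out of the long-term tables. They remain TEAEs in the cumulative period, with severity, relationship, interruption and discontinuation tabulated. Whether the serious flag is lost depends partly on the SAE rules and follow-up of Studies 109 and 011B, which are not in these documents.
- **Protocol 11.6.7.2 is not a second exemption.** It says: "If the hospitalization is unplanned, the procedures for safety reporting should also be followed". A reader might take this to confine safety reporting to unplanned stays. It does not say so; it concerns outcome events in Study 109 subjects, records dates and reasons for planned stays too, and does not override 13.1.2.1 or 13.1.2.3.
- **The Observational Cohort is exposed only in the same narrow case.** A child who stopped drug had to stay in the parent study to Week 24 or 26. The admission must have been arranged by consent and still be outstanding.

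None of this changes the reference date. The exemption still reaches back over on-drug time, and no provision corrects it.

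**Conclusion.** The point holds as a defect of definition with a limited effect. Read as written, 13.1.2.1 lets a pre-planned admission for an event that arose on parent-study LUM/IVA go without serious status in Study 110, which sits badly with Protocol 13.1.1.3 and SAP 9.1.3. In the Treatment Cohort the possible loss is a serious flag in the cumulative L200/I-L/I data, and hence in L/I Overall. In the Observational Cohort it may be the whole Study 110 record of the event.

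The number of children affected is not in the documents and is probably small. No overall understatement in percentage points can be derived, and any assumed count of children would be only that. The per-event figure of about 0.16 to 0.17 per 100 patient-years rests on full enrolment, full exposure and the assumed placebo range. The direction is certain: the exemption can remove SAEs and cannot add any.

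**What to change.** In Protocol 13.1.2.1, the exemption uses the words *signed the ICF* twice. In both places replace them with *signed the ICF for the previous study (Study 109 or Study 011B)*. Conditions and plans that pre-date parent-study participation stay exempt; events that arise during it do not. The provision for stays hastened or prolonged by an AE can remain as it is, and Protocol 11.6.7.2 needs no edit.

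The cost is a short wording change, a few more SAE forms and a slightly less favourable SAE count. Dosing, visits, sample size and analysis methods are not affected.
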